## 3 Study design

This is a non-randomized, open-label, multi-center, phase II study to assess the efficacy and safety of eltrombopag in Chinese subjects with severe aplastic anemia who had insufficient

response or relapsed following at least one treatment course in the period time of  $> 6$  months of immunosuppression with a regimen containing anti-thymocyte globulin (ATG), anti-lymphocyte globulin(ALG), and/or cyclophosphamide, or alemtuzumab. The study design is shown in [Figure 3-1](#).

As this is a bridging study to support China registration, an estimation strategy rather than formal hypothesis testing will be pursued. Approximately 20 subjects will be enrolled into the study based on feasibility and statistical considerations.

Treatment with eltrombopag will be started at 25 mg/day and increased by 25 mg/day every 2 weeks according to the platelet count up to 150 mg/day (Refer to [Section 6.5.1](#)). Hematological response rate will be assessed at 3, 6 months and 1 year after starting the study treatment (Week 13, 26 and 52).

The primary endpoint is the hematologic response rate (defined as the proportion of subjects who meet any of the IWG response criteria) at Week 26. Subjects in whom the treatment is assessed as effective (meet any of the response criteria) at 6 months will continue the study treatment.

Eltrombopag should be discontinued if the treatment is assessed as ineffective at 6 months in order to avoid continuing treatment aimlessly. Subjects are allowed to discontinue eltrombopag before 6 months if any of the treatment discontinuation criteria described in [Section 9.1.1](#) is met.

[figure not shown]

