#### 6.1.5 Treatment duration

If the subject fails to response after 6 months (26 weeks), he/she will discontinue eltrombopag treatment. Responding subjects who are considered to require continued treatment at Week 52 will be provided with continued treatment up to the launch of the product after approval of the investigated indication or until the end of the study.

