## Clinical laboratory evaluations

All laboratory data will be listed by subject and visit/time and if normal ranges are available abnormalities will be flagged. Summary statistics will be provided by visit/time.

Grading of laboratory values will be assigned programmatically as per National Cancer Institute (NCI) Common Terminology Criteria for Adverse Events (CTCAE) version 4.03 or the latest version at the time of the analysis. The calculation of CTCAE grades will be based on the observed laboratory values only, clinical assessments will not be taken into account.

CTCAE Grade 0 will be assigned for all non-missing values not graded as 1 or higher. Grade 5 will not be used.

For laboratory tests where grades are not defined by CTCAE, results will be categorized as low/normal/high based on laboratory normal ranges.

The following summaries will be generated separately for hematology, and chemistry tests:

- Listing of all laboratory data with values flagged to show the corresponding CTCAE grades if applicable and the classifications relative to the laboratory normal ranges

For laboratory tests where grades are defined by CTCAE:

- Worst post-baseline CTCAE grade (regardless of the baseline status). Each subject will be counted only once for the worst grade observed post-baseline.
- Shift tables using CTCAE grades to compare baseline to the worst on-treatment value

For laboratory tests where grades are not defined by CTCAE:

- Shift tables using the low/normal/high/ (low and high) classification to compare baseline to the worst on-treatment value.

In addition, regardless of the transfusion or G-CSF, laboratory tests (Platelet counts, Hemoglobin, Neutrophil count) value and change from baseline will be listed and summarized in scheduled visits using descriptive statistics (mean, standard deviation, median, interquartile range, and range)

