2.5.1 Primary endpoint

The primary endpoint is the hematologic response rate at Week 26, which is defined as the proportion of all subjects who meet any of the International Working Group (IWG) criteria at Week 26 shown in the table below. The primary endpoint will be based on the investigator assessment of response.

The analysis for primary endpoint as well as related supplementary and supportive analysis will not be reproduced for final CSR.

The primary analysis will be based on FAS and will include all data observed up-to the cut-off date.

Table 2-2 IWG criteria for Primary Endpoint

Assessment Item	Baseline transfusion status	Response Criteria
Platelet count	Platelet transfusion independent	Transfusion independent ⁽¹⁾ and increase from baseline by $20 \times 10^9/L$ or more
	Platelet transfusion dependent	No platelet transfusion requirement for 8 weeks
Hemoglobin	RBC transfusion independent	When the baseline hemoglobin level is < 90 g/L: transfusion independent and increase from baseline by 15 g/L or more
	RBC transfusion dependent	A decrease of at least 4 units in RBC transfusions in the post-treatment 8-week period (1 unit = RBC derived from 200 mL blood) Or no RBC transfusion requirement for 8 weeks (less than 4 units RBC in 8-week period at Baseline)

Assessment Item	Baseline transfusion status	Response Criteria
Neutrophil count	NA	(In the absence of G-CSF taken within 21 days preceding the blood sample collection) Increase from baseline by $0.5 \times 10^9/L$ or more, or (if $< 0.5 \times 10^9/L$ at baseline) increase by 100% or more

Note: No platelet/RBC transfusion requirement for 8 weeks means there is no any platelet/RBC transfusion received by patients during (Visit date-56 days) until Visit date. This definition also applies to Week 13 and Week 52.

(1) Transfusion independent means subjects did not receive platelet transfusion in the 4 weeks before Visit date.

During regular hematologic assessment, the exclusion period of transfusion and G-CSF are detailed below:

Platelet transfusion: 7 days preceding the assessment of platelet count

RBC transfusion: 14 days preceding the assessment of hemoglobin

G-CSF: 21 days preceding the assessment of neutrophil count

Definition of baseline Platelet Transfusion Independence/Dependence and platelet count

Baseline platelet transfusion independence/dependence and platelet count are defined as:

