For subjects receiving platelet transfusion at baseline, the frequency and the amount of platelets transfusion in each period (Baseline: 4 weeks before Day 1; Week 13, 26, 52: 4 weeks before each visit day) will be summarized. The same analysis applies to RBC transfusion (period will be extended to 8 weeks). The amount of transfusion will be defined as the sum of transfusion multiplied by the volume of transfusion.

The analysis for frequency and amount of transfusion will not be reproduced for final CSR.

Proportion of subjects with transfusion decrease

Subjects with platelet transfusion decrease is defined as subjects with transfusion decrease or transfusion free in each period (Week 13, 26, 52: 4 weeks before each visit day) compared to baseline (Baseline: 4 weeks before Day 1). 50% platelet transfusion reduction is defined as subjects with transfusion decrease of amount (units) at least 50% compared to baseline. The same analysis applies to RBC transfusion (period will be extended to 8 weeks). This analysis will be performed for the subgroup of subjects with baseline transfusion dependent.

The analysis for proportion of subjects with transfusion decrease will not be reproduced for final CSR.

Maximum duration of Platelet and RBC transfusion independence

Transfusion independence duration will be defined as the period from the next day of transfusion to the day before the next transfusion. Maximum duration of platelet and RBC transfusion independence for each subject will be picked for analysis.

Post-baseline transfusion independence will be achieved if subjects who are transfusion dependent at baseline become transfusion free for a period of at least 28 (platelets) or 56 days (RBCs). The time period for assessment of transfusion independence will be at any time during the treatment period. Baseline platelet and RBC transfusion dependence is defined as subjects receiving at least one platelet or RBC transfusion in the 4 weeks and 8 weeks, respectively, prior to the first dose of eltrombopag.

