2.7.2 Statistical hypothesis, model, and method of analysis

Hematological Response at Week 13 and Week 52

The number and percentage of subjects who meet the hematological response criteria (at Week 13 and Week 52 respectively) will be presented and exact 90% confidence interval will be reported. And the number and percentage of assessment item for the hematological response criteria and for the detailed hematological response criteria will be presented.

The derived response by programming at week 13 and Week 52 will also be summarized as above.

Changes in platelet count, hemoglobin and neutrophil count

Values and changes in platelet count (in the absence of platelet transfusion), hemoglobin (in the absence of RBC transfusion) and neutrophil count (in the absence of G-CSF) will be summarized at each visit. Descriptive statistics including mean, SD, median, 25th and 75th percentiles, minimum, and maximum will be summarized for the changes.

Median and interquartile range will be plotted.

Time to hematological response

The distribution function of time to hematologic response will be estimated using the Kaplan-Meier method and will be plotted. The median time to hematologic response along with 90% CIs will be presented. If a subject does not meet hematological response before or at the cutoff date, censoring will be performed using the date of the last assessment.

Duration of hematological response

The distribution function of duration of hematologic response will be estimated using the Kaplan-Meier method and will be plotted. If the number of relapses or deaths allows, the median time to hematologic response along with 90% CIs will be presented.

Relapse-free probability will be estimated using the Kaplan-Meier method at 3 months, 6 months, 9 monthes, one year, and yearly after as well.

Frequency and amount of transfusion

The frequency and the amount of platelets transfusion in each period (Baseline: 4 weeks before Day 1; Week 13, 26, 52: 4 weeks before each visit day) will be summarized by descriptive statistics including mean, SD, median, 25th and 75th percentiles, minimum, and maximum.

Proportion of subjects with transfusion decrease

The number and percentage of subjects with platelet or RBC transfusion decrease or transfusion-free in each period will be presented.

In addition, the number and percentage of subjects with 50% platelet or RBC transfusion reduction in each period will be presented.

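### After Week 26 the count-change summaries follow almost only continuing responders, so they can show a rise that no subject had; separately, the protocol's all-values change summary is missing from the SAP and its removal is not declared

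*SAP*

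**What the plan says.** **Count changes.** This secondary endpoint covers platelets, hemoglobin and neutrophils. For the last two, SAP 2.7.2 says "hemoglobin (in the absence of RBC transfusion) and neutrophil count (in the absence of G-CSF) will be summarized at each visit"; the same sentence restricts platelets to values free of platelet transfusion. Medians and interquartile ranges are plotted. SAP 2.7.1 lists this among the few efficacy analyses generated for the final CSR.

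**Exclusion windows (SAP 2.5.1).** For platelets: "Platelet transfusion: 7 days preceding the assessment of platelet count". The corresponding windows are 14 days for hemoglobin after an RBC transfusion and 21 days for neutrophils after G-CSF.

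**Who remains after Week 26.** Protocol 3: "Eltrombopag should be discontinued if the treatment is assessed as ineffective at 6 months". Protocol 6.1.5: "If the subject fails to response after 6 months (26 weeks), he/she will discontinue eltrombopag treatment". Protocol 6.5.1, below Table 6-5, takes such subjects off study. Protocol 9.1.1 leaves a discontinuation visit and a follow-up visit, and Protocol 3 puts the latter 30 days after stopping.

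**Transfusion use.** SAP 2.7.1: "For subjects receiving platelet transfusion at baseline, the frequency and the amount of platelets transfusion in each period" is summarized, with look-back periods before Weeks 13, 26 and 52. RBC transfusion is handled alike over 8 weeks. This output is not repeated for the final CSR.

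**Missing data.** SAP 2.7.3 gives rules for response, time to response and duration of response. It gives none for count changes or for transfusion frequency and amount.

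**The all-values summary.** Protocol 12.5.2: "In addition, regardless of the transfusion or G-CSF, laboratory tests (Platelet counts, Hemoglobin, Neutrophil count) value and change from baseline will be listed"; the sentence goes on to require descriptive statistics by scheduled visit. The nearest item in SAP 2.8.3 is box plots, with supporting tables, of values for selected parameters that are not named. SAP Section 4 reports no departure from the protocol's analyses.

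**The concern.** A reader of the final CSR will see a median line running from baseline through Week 26 and on to later visits, and will read it as the course of one group. It is not one group. Up to Week 26 it describes everyone still under treatment. Afterwards it describes those who met a response criterion at Week 26, and response is itself defined by these counts and by transfusion need. The composition changes at a fixed time, in a known direction, and by more than half the sample at the planned 40% response rate. An upward step would look like deepening response under continued treatment, in a single-arm study with no comparator to expose it.

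Transfusion frequency and amount at Week 52 can fall in the same way, because baseline-transfused subjects who did not respond are no longer measured.

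The missing all-values summary is a separate matter. The protocol pairs a transfusion-free view of the counts with an unrestricted one. The SAP keeps only the first for change from baseline and does not say that the second was dropped.

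**Working it through.** **1. The plan's own figure.** The plan gives no figure for these summaries; its only sizing figure is the exact 90% interval for the response rate. With x responders of n = 20, the Clopper-Pearson limits are the 0.05 quantile of Beta(x, n−x+1) and the 0.95 quantile of Beta(x+1, n−x). For x = 8 this gives 21.7% to 60.6%. The largest half-width is 19.8 points, at x = 10. Both match SAP 3.1, as do the other rows of Table 3-1.

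**2. Who contributes.** With x responders at Week 26, about x subjects supply later scheduled visits and 20 − x do not, apart from one visit about 30 days after stopping.

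**3. Size under stated assumptions.** Let R be the mean change in responders, NR the mean change in non-responders and p = x/20. The mean over all subjects is pR + (1−p)NR; over continuing responders it is R. Assume R = +30, NR = 0, nobody changing after Week 26, and no other losses. R and NR are not in the documents; the response rates are those of SAP Table 3-1.

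| Responders of 20 | Leave | Mean, all 20 | Mean, continuing | Ratio |
|---|---|---|---|---|
| 4 (20%) | 16 | 0.2 × 30 = +6 | +30 | 5.0 |
| 6 (30%) | 14 | 0.3 × 30 = +9 | +30 | 3.3 |
| 8 (40%) | 12 | 0.4 × 30 = +12 | +30 | 2.5 |
| 10 (50%) | 10 | 0.5 × 30 = +15 | +30 | 2.0 |

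With NR = 0 the ratio is 1/p, whatever R is. If NR = +5 at 40%, the all-subject mean is 12 + 0.6 × 5 = +15 (ratio 2.0). If NR = −5, it is 12 − 3 = +9 (ratio 3.3).

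For the median, a simulation with 8 responders at +30 (SD 15) and 12 non-responders at 0 (SD 8), all assumed, gave about +6.5 for the 20 subjects and +30 for the 8.

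**4. Chance selection with no drug effect.** Neutrophils were simulated with median 0.5 × 10⁹/L, between-subject log SD 0.5 and within-subject CV 20% to 50% (all assumed), using only the neutrophil criterion. Between 1.5% and 17% of subjects qualified by chance. Their later mean change was +0.20 to +0.25 × 10⁹/L, against 0.00 in all subjects.

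**5. The exclusion windows.** Platelets were simulated with no drug effect: median 14 × 10⁹/L, between-subject log SD 0.4 to 0.7, within-subject CV 20% to 60%, and transfusion when the count a week before was below 10 (variability and median assumed). Between 23% and 43% of values were excluded. The mean kept value was 1.7 to 4.0 × 10⁹/L above the mean of all underlying values, but the mean change was only 0.03 to 1.2 × 10⁹/L higher. For changes, loss of non-responders is the larger issue.

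**6. The two documents side by side.** Protocol 12.5.2 asks for value and change from baseline, three named counts, scheduled visits and no transfusion exclusion. SAP 2.8.3 uses all available assessments and shows values over time, but names none of the counts and gives no change from baseline. The two differ, and SAP Section 4 says they do not.

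**The case against.** The case against has real weight.

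- **The exclusion is the endpoint.** Absence of transfusion or G-CSF is written into Protocol Table 2-1 and SAP 1.2, and it keeps transfusion-inflated counts from passing as drug effect. This stands. A reader might infer that the exclusion itself manufactures improvement; the documents do not support that, and step 5 suggests little effect on changes.
- **Transfusion summaries drop no transfused values.** A reader might infer that they do; in fact transfusions are what they count. For the transfusion-decrease percentages, SAP 2.1.2 keeps the whole baseline-dependent subgroup as denominator. What remains is the loss of non-responders from Week 52 frequency and amount.
- **The illustration is assumed and simplified.** Response in any lineage counts. If only 4 of 8 responders gained +30 in platelets, the means would be 4 × 30/20 = +6 and 4 × 30/8 = +15: a smaller step, though the same ratio. If 6 of 12 non-responders were already excluded at Week 26 for transfusion, that mean would be 8 × 30/14 = +17. So the summaries can rise; it does not follow that they will.
- **Some protection exists.** SAP 2.3.5 reports disposition, SAP 2.8.3 gives partial all-values displays and listings, and the protocol summary plans n for the remaining endpoints. None of these shows the same subjects at Week 26 and later, and the statistics listed in SAP 2.7.2 do not include n.
- **The all-values summary does not cure drop-out.** Correct: it loses the same subjects after Week 26, so the two issues need separate remedies.

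**Conclusion.** The point holds for descriptive secondary summaries. After Week 26 the count-change tables and plots describe almost only Week 26 responders, and SAP 2.7 neither labels nor handles this. Week 52 transfusion frequency and amount share the problem, at the updated analysis only. The direction follows whenever responders have larger changes than non-responders. The size cannot be derived from the documents: +12 to +30 at 40% response, and a ratio of 5.0 to 2.0 across 20% to 50%, rest on assumed mean changes of +30 and 0.

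The omission of the Protocol 12.5.2 summary needs no assumption. It is a discrepancy between the documents, and SAP Section 4 is inaccurate as it stands.

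A reader might infer that the main efficacy result is compromised. It is not: discontinuation before Week 26 counts as non-response for the primary endpoint (SAP 2.5.3), and a missing Week 52 response counts as non-response unless the subject is ongoing and has not yet reached that visit (SAP 2.7.3). Count summaries at Weeks 13 and 26 are also untouched by the Week 26 stop.

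**What to change.** 1. Add to SAP 2.8.3 the Protocol 12.5.2 summary of value and change from baseline for platelets, hemoglobin and neutrophils regardless of transfusion or G-CSF, beside the transfusion-free version. Otherwise, declare its removal and correct SAP Section 4.
2. For visits after Week 26, show baseline, Week 26 and later values for the same subjects, labelled as continuing subjects (Week 26 responders). Do the same for transfusion frequency and amount wherever Week 52 data are reported, and state how subjects without Week 52 transfusion data are handled.
3. At each visit print the number contributing, the number excluded for recent transfusion or G-CSF, and the number off study.

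No new data are needed. For the final CSR this means one added laboratory table, one panel and a few rows. The transfusion panel belongs with the updated analysis; because that output is not planned for the final CSR, adding it there would mean reopening it.
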